DLT is defined as occurrence of any treatment-emergent adverse event (TEAE) as described in Section 8.1.3 during the DLT assessment window, unless clearly unrelated to the study drug as per investigator's discretion.

DLT Assessment Window:

For all patients in dose escalation, DLTs will be assessed during the DLT assessment window. This is the first 28 days of continuous study treatment (C1D1 through C1D28), and does not include the dose administered during PK week.

DLT-Evaluable Patient:

A patient is DLT-evaluable if the following criteria are met:

- has received at least 75% of the assigned dose of study drug during the DLT assessment window

OR

- has not completed DLT assessment period due to a DLT

For decisions on dose escalation, each dose cohort shall present the protocol-required numbers of DLT-evaluable patients. Patients who are not DLT-evaluable in a dose cohort may be replaced to guarantee the protocol-required number of DLT-evaluable patients for dose escalation evaluations.

Patients who complete the DLT assessment window will be allowed to continue treatment until disease progression, intolerable toxicity, withdrawal of consent, lost to follow-up, end of study, conditions are met per Section 6.2.1, or death, whichever comes first.

Maximum Tolerated Dose

The MTD determination will be driven by the mTPI-2 method. The MTD will be any doses with true toxicity probability in the equivalence interval. For this study, the equivalence interval is defined as 15% to 25%.

Recommended Dose of the Expansion Cohort and Phase 2 Clinical Study (RP2D)

RP2D determination will take the following criteria under consideration:

- Determination of MTD achieved during the dose escalation part
- Assessment of safety, PK, and PD

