7.5 Dose Adjustments

7.5.1 Adjustment of Dose Within the DLT Assessment Window

In the DLT assessment window, patients without DLT must not undergo dose reduction of HMPL-306.

- If a DLT occurs, HMPL-306 administration will be suspended and appropriate supportive treatment will be given.
- If a DLT returns to Grade 1 (inclusive) or lower within 14 days, HMPL-306 may be resumed at the previous lower dose if the investigator assesses that the patient may still benefit.
- If a DLT has not returned to Grade 1 (inclusive) or lower within 14 days, or DLT reoccurs at the lowered dose, HMPL-306 treatment will be terminated.
- If a patient experiences a Grade 4 nonhematologic toxicity, HMPL-306 treatment will be terminated.

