9.1.3 Analysis Sets

The following analysis sets are defined for this study:

- Safety analysis set: All enrolled patients who received at least 1 dose of study treatment will be included in safety analysis population. Safety evaluation will be performed based

on first dose of study treatment received by a patient. This is the primary population for safety and efficacy analyses.

- DLT-evaluable analysis set: All patients enrolled in dose escalation part who are evaluable for DLT assessment. A patient is DLT-evaluable if such a patient meets the following criteria:
 - Has received at least 75% of the assigned dose of study drug during DLT assessment window
 - OR
 - Has not completed the DLT assessment period due to a DLT
- Response (efficacy) evaluable analysis set: All patients who receive study treatment and have a baseline tumor assessment, followed by at least 1 post-baseline assessment (usually after C3D1) will be considered evaluable for antitumor clinical response or efficacy endpoints.
- PK analysis set: All patients with at least 1 quantifiable plasma concentrations of HMPL-306 will be included in PK population analysis.
- PD analysis set: All patients with at least 1 quantifiable level of 2-HG in plasma will be included in PD population analysis.

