7. CHANGE FROM THE PROTOCOL

Here is a list of changes in this analysis plan compared with the protocol

- Added All Subject Set for pre-screening and screening summaries.
- Added Efficacy Analysis Set as primary analysis set for efficacy analysis and clarified definition of Response Evaluable Analysis Set as single dose from the PK week might not be an effective treatment. Safety Analysis Set was the primary set for safety analysis.
- The DLT- evaluable analysis set definition in the protocol is to include all patients enrolled into dose escalation part of the study who (i) either received at least 75% of the assigned doses of the HMPL-306 during the DLT assessment window (i.e. Cycle 1 Day 1 [C1D1] through C1D28) or (ii) experienced a DLT in Cycle 1. However, since these criteria have been incorporated in the SRC review, the DLT-evaluable analysis set will be based on the decision from the SRC review.
- Removed DLT-equivalent analysis as investigator's evaluation of each AE satisfying DLT criteria or not was not well documented in EDC.
- Patients enrolled were summarized based on all subject set instead of safety analysis set.
- Removed Rate of CR+CRh, duration of CR+CRh and time to CR+CRh endpoints, since cCR-2 (rate of CRM RD+CR+CRh) and cCR-3 (rate of CRM RD+CR) are more meaningful.
- Removed Time to Hematologic Recurrence endpoint as it has the similar rationale for DOcCR1.
- Removed Disease Free Survival (DFS) endpoint as it has the same rationale for DOcCR1.

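### A patient with a DLT who resumes at a lower dose and completes Day 28 on less than 75% of the assigned dose is not DLT-evaluable under the protocol wording, and the protocol and SAP disagree on whether that DLT counts

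*Protocol*

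**What the plan says.** **Evaluability.** Protocol Section 4.1.1 gives two alternative limbs. The first, on exposure, is that the patient "has received at least 75% of the assigned dose of study drug during the DLT assessment window". The second limb, on toxicity, is met by a patient who "has not completed DLT assessment period due to a DLT". Section 9.1.3 uses the same two limbs for the analysis set, the second being "Has not completed the DLT assessment period due to a DLT". Section 4.1.1 requires each cohort to present the required number of DLT-evaluable patients for escalation decisions. It and Section 6.2.1.4 allow non-evaluable patients to be replaced.

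**Window.** Section 4.1.1: "This is the first 28 days of continuous study treatment (C1D1 through C1D28), and does not include the dose administered during PK week".

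**What happens at a DLT.** Section 7.5.1: "If a DLT occurs, HMPL-306 administration will be suspended and appropriate supportive treatment will be given". It continues: "If a DLT returns to Grade 1 (inclusive) or lower within 14 days, HMPL-306 may be resumed at the previous lower dose", subject to the investigator's view that the patient may still benefit. Treatment ends if the DLT has not recovered within 14 days, if it recurs at the lowered dose, or if a nonhematologic toxicity is Grade 4.

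**What the decision table counts.** The note to Table 5 describes the axes as patients treated at the dose and DLTs observed. The text of Section 4.1.1 likewise speaks of patients dosed and DLTs experienced. Neither is limited to evaluable patients.

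**SAP.** Section 7 reports the protocol's second limb as "experienced a DLT in Cycle 1", with no condition about completing the window. It adds that the criteria have been built into SRC review. Section 3.1.3 therefore defines the DLT-evaluable set by the SRC's decision for each cohort. Section 5.2.11.1 bases all DLT summaries on that set.

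**The concern.** The protocol's second limb asks for two things together: a DLT, and failure to complete the window because of it. Section 7.5.1 opens a path on which the first is true and the second is not: a DLT, a hold, recovery, resumption at a lower dose, and Day 28 reached. That patient is evaluable only through the 75% limb, and the hold and the lower dose both count against that limb.

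Patients whose DLT ends treatment inside the window are caught by the second limb. The patients exposed to the gap are those with reversible DLTs and a hold long enough, or early enough, to bring exposure below 75%. For them, a literal reading removes an observed DLT from both numerator and denominator and allows a replacement. The resulting error runs one way, towards escalation. DLTs and the MTD/RP2D are primary endpoints of Part 1, and the same set supplies the reported DLT rate.

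**Working it through.** **1. Reproduce Table 5.** Inputs from the protocol: target 20%, equivalence interval 15% to 25%. Standard settings that the documents do not state: Beta(1,1) prior, and DU when P(p > 0.20 | data) > 0.95. With sub-intervals of width 0.10 and the largest unit probability mass, 52 of the 54 cells in rows 0 to 4 are reproduced. The two that differ are 1/1 (table D, computed DU) and 2/8 (table S, computed D, with the posterior mode exactly on the 0.25 boundary). Neither bears on this point. The cells that matter all agree: 0/3 = E, 1/3 = D, 1/4 = D, 1/5 = S, 2/6 = D.

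**2. Who falls below 75%.** Let d be the first held day, h the number of days held, and f the ratio of the lower dose to the assigned dose. Then

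exposure = [(d − 1) + f × (28 − (d − 1) − h)] / 28.

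The doses are redacted, so f is an assumption, shown from 0.5 to 0.8. Assigned dose is taken to mean the cohort's dose.

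- Hold of more than 7 days, ignoring any dose reduction (f = 1): at most (28 − 8)/28 = 71.4%. Below 75% for every d.
- Hold of 7 days, then any reduced dose: always below 75%. For d = 8: f = 0.5 gives (7 + 7)/28 = 50.0%; f = 0.8 gives (7 + 11.2)/28 = 65.0%.
- Hold of 14 days from d = 8: f = 0.5 gives (7 + 3.5)/28 = 37.5%; f = 0.8 gives (7 + 5.6)/28 = 45.0%.
- Hold of 3 days from d = 22, f = 0.5: (21 + 2)/28 = 82.1%. Still evaluable.
- Hold of 3 days in general: below 75% only if d ≤ 17 (f = 0.5), d ≤ 13 (f = 0.67) or d ≤ 5 (f = 0.8).

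If assigned dose were read as the reduced dose after resumption, f = 1 applies and only holds of more than 7 days fail.

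**3. Effect on the decision (cells read from Table 5).**

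| All DLTs counted | One DLT patient left out | Change |
|---|---|---|
| 1/4 = D | 0/3 = E | de-escalate to escalate |
| 2/6 = D | 1/5 = S | de-escalate to stay |
| 1/3 = D | 0/3 = E, after replacement by a patient without a DLT | de-escalate to escalate |

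**4. Illustration of size.** With true DLT rate p, P(0/3) = (1 − p)³. If a share q of DLT patients is left out and replaced, the effective rate is p(1 − q)/(1 − pq). The documents give no value for q; 0.25 and 0.5 are illustrative.

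| p | q = 0 | q = 0.25 | q = 0.5 |
|---|---|---|---|
| 20% | 51.2% | 59.7% | 70.2% |
| 30% | 34.3% | 43.3% | 55.9% |
| 40% | 21.6% | 29.6% | 42.2% |

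For example, p = 0.30 and q = 0.5 give 0.15/0.85 = 0.1765, and (1 − 0.1765)³ = 55.9%.

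**The case against.** The other side has five arguments.

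- **The path is narrow.** Section 7.5.1 ends treatment for unresolved, recurrent and Grade 4 nonhematologic DLTs, and Section 7.5.4 points to discontinuation for delays of 14 days or longer. Those patients, if stopped in the window, count. This stands for the 14-day case, which sits on that boundary. It does not remove holds of 8 to 13 days, or a 7-day hold followed by a lower dose.
- **A hold may itself be non-completion.** The window is described as continuous treatment, so a suspended patient arguably has not completed it. The reading is possible, and the SAP's restatement is consistent with it. But the same sentence fixes the window as C1D1 through C1D28, and whether a DLT counts should not rest on an inference.
- **The decision table counts observed DLTs.** The Table 5 note and the surrounding text would keep the DLT. This stands: the documents conflict, and they do not uniformly drop the event.
- **The SRC reviews everything.** Section 6.2.2.2 bars escalation until the SRC has seen all available cohort data, Section 8.2.3 requires DLTs to be reported within 2 business days, and replacement is optional. An unnoticed reversal is therefore less likely. These steps do not settle which rule defines the set.
- **Escalation is over.** The SAP reports one expansion patient, who is pooled with Cohort 8. Editing the protocol cannot change decisions already taken. This stands, and it makes the SAP text the more urgent part.

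A reader might infer that the SRC was told to apply the protocol's narrower limb. No section says so. SAP Section 7 refers to criteria built into SRC review immediately after stating the broader version.

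**Conclusion.** The gap is real on the literal wording of Protocol Sections 4.1.1 and 9.1.3, given Section 7.5.1. It is limited to patients with a DLT who resume at a lower dose, complete Day 28 and received less than 75% of the assigned dose. For them an observed DLT can leave the count, and one such omission is enough to turn D into E or S in Table 5. The SAP misreports the protocol limb and leaves the set to SRC decisions, so the two documents do not give one rule.

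Two stronger readings are tempting. The first is that every DLT patient who resumes and finishes is dropped. That is wrong, because the 75% limb keeps those with short or late holds. The second is that the escalation was in fact biased. Nothing in the documents shows that a DLT was left out, and Section 4.1.1 reports none at dose levels 1 to 3, so any real effect could concern only higher levels. The size cannot be fixed: dose ratios are redacted, and the share of DLT patients affected is unknown. The probabilities above rest on assumed values.

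**What to change.** - **Protocol Sections 4.1.1 and 9.1.3:** replace the second limb so that any patient with a DLT in C1D1 to C1D28 is DLT-evaluable whatever dose was received. State there and in Section 6.2.1.4 that such a patient is not replaced.
- **Note to Table 5:** align it with this, so that the table and the evaluability rule count the same patients.
- **SAP Section 3.1.3:** state the same rule explicitly, in addition to the reference to SRC decisions. **SAP Section 7:** describe the protocol limb as it is written and record the change.
- **Before database lock:** check the SRC decision for each cohort for any patient with a DLT in the window who was classed as non-evaluable or replaced, and report the result.

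This changes no dosing rule. The cost is a few lines of text, one check of existing records, and an observed DLT rate that may be slightly higher.

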4.1.2 Part 2 (Dose Expansion)

In the dose expansion part, HMPL-306 will be administered at the MTD and/or RP2D to evaluate further the safety, tolerability, PK, PD, and preliminary efficacy in approximately 10 patients with advanced relapsed, refractory, or resistant hematological malignancies with IDH mutations.

Patients enrolled in the dose expansion part must not have standard therapeutic options available (including IDH inhibitors where approved) and must have the following:

- Relapsed AML unsuitable for intensive chemotherapy or venetoclax-based regimen or target agents;
- Primary refractory AML unsuitable for intensive chemotherapy or venetoclax-based regimen or target agents;
- Relapsed/refractory AML that has progressed on prior IDH treatment

The sponsor, in consultation with SRC, may decide to increase or decrease the number of enrolled patients depending on preliminary clinical response, safety signals, or operational feasibility. Patients who are not efficacy evaluable in any cohort may be replaced.

Study Treatment

Patients will receive HMPL-306 daily at **CCI** mg QD (highest tolerable dose evaluated in the dose escalation part) for 28-day cycles until disease progression, death, intolerable toxicity, withdrawal of consent, lost to follow-up, conditions are met per Section 6.2.1, or end of study, whichever comes first.

Safety Monitoring

Continuous safety monitoring for all enrolled patients will be carried out by participating investigators and the sponsor. The severity of all AEs will be graded in accordance with National Cancer Institute (NCI) Common Terminology Criteria for Adverse Events (CTCAE) version 5.0.

4.2 Design Rationale

4.2.1 Rationale for Starting Dose and Dosing Regimen

HMPL-306 is intended for use in patients with advanced relapsed, refractory, or resistant hematological malignancies. Hence, the starting dose is calculated based on the S9 guidelines from ICH of Technical Requirements for Registration of Pharmaceuticals for Human Use, using the HNSTD, and NOAEL dose (female). The calculation method is shown in [Table 6](#) below:

Table 6 Starting Dose Calculation

	A 4-Week Study of HMPL-306 Orally Administered to SD Rats With an CC1 Recovery Period	A 4-Week Study of HMPL-306 Orally Administered to Beagles With an CC1 Recovery Period
Animal dose (mg/kg)	HNSTD CC1	Female: NOAEL= CC1 Male: HNSTD= CC1
Equivalent dose ratio converted based on body surface area (human/animal)	CC1	
Equivalent dose in human body converted based on body surface area (mg/kg/day)		
Equivalent dose in 60 kg of human body converted based on body surface area (mg/day)		
Initial dose calculated based on ICH S9 (mg/day)		
Proposed initial dose of phase I clinical trial (mg/day)		
Safety factor		

HNSTD=highest nonseverely toxic dose; ICH=International Council for Harmonization, NOAEL=no-observed-adverse-effect level; SD=Sprague-Dawley

The HNSTD was calculated from repeated dose toxicology studies in ruminant (rat) and non-ruminant (dog), and it showed safe doses obtained that were equivalent to human skin surface area dosages of **CC1** mg/day (rat) and **CC1** mg/day (dog). In accordance with ICH S9, the initial dose for first-in-human (FIH) study should be 1/10 of HNSTD in rats or 1/6 of HNSTD in dogs. Consequently, the starting dose calculated for the FIH study should be **CC1** mg/day or **CC1** mg/day. Nevertheless, initial dose for this FIH phase 1 clinical study is set at **CC1** mg QD PO. This provides a safety window of more than 14 times and about 39 times as calculated from the results of these studies in rats and dogs, respectively.

Furthermore, and in accordance with ICH S9, the dosing interval of the FIH study should be based on the dosing interval of nonclinical repeat-dose toxicity studies and the estimated half-life in the human body. The dosing interval of HMPL-306 in the 4-week repeated dose toxicity studies was QD. The estimated half-life of HMPL-306 was similar to that of approved products on market, which all use a regimen of QD. Therefore, a regimen of QD will be initially explored in this study. Exploration of another dosing regimen may be implemented, if indicated, based on analysis of emerging data.

4.2.2 Rationale for Study Population Selection

Mutations involving IDH enzymes play a role in the pathogenesis and development as subset of some hematological malignancies such as AML, MDS, MPN, and AITL. IDH mutations have been reported in 7% of MDS cases, 3% to 4% of MPN cases, and 20% to 30% of AITL cases

([Tefferi 2010](#), [Breems 2008](#), [Cairns 2012](#), [Wang 2015](#), [Yonal-Hindilerden 2016](#), [Wang 2017](#)). These mutations are critical in patient selection, clinical response, and even prognosis of these patients. Currently, ivosidenib (mIDH1 inhibitor) and enasidenib (mIDH2 inhibitor) are the only approved treatments available for patients in the United States with relapsed/refractory AML that harbor IDH1 and/or IDH2 mutations. Therefore, this study plans to enroll patients that harbor IDH mutations, co-mutation, or any combination thereof. Discussion of rationale including specific hematological malignancies for which IDH1 and/or IDH2 mutations play a role in some cases of disease, appears in the following sections.

4.2.2.1 Relapsed/Refractory Acute Myeloid Leukemia

This study plans to enroll AML patients who have received at least 1 prior line of therapy. The median overall survival for patients with refractory AML is 1.5 months with only 8% one-year survival ([Giles 2005](#)). Current guidelines recommend enrollment in a clinical trial for the management of relapse and/or refractory AML.

For patients with IDH mutations who are ineligible for standard chemotherapy and have failed standard of care first-line treatment (eg, low-dose cytarabine or HMA in combination with venetoclax), and for whom targeted therapy or salvage chemotherapy is not appropriate or have not had IDH isoform switching after prior treatment with IDH inhibitor, current guidelines recommend a clinical trial ([NCCN-AML 2021](#), [Heuser 2020](#)).

Treatment options for primary refractory and relapsed AML in those patients who have undergone prior standard induction chemotherapy and consolidation, including allogeneic hematopoietic stem cell transplantation (allo-HSCT) and are not fit for further intensive or targeted treatment is limited. In the event that no clinical study is available, then the intent of second salvage chemotherapy in these patients, however, is only supportive at best.

Patients who have received at least 1 prior line of therapy, where an established standard of care with proven benefit for which the patient is eligible is not available at the time of enrollment, is an appropriate population for this 2020-306-GLOB1 study.

4.2.2.2 Relapsed/Refractory High-Risk Myelodysplastic Syndrome

This study plans to enroll HR-MDS patients who have relapsed after or are refractory to first-line treatment. High-risk MDS carries a major risk of progression to AML and short survival. Treatment options at diagnosis are limited to allo-HSCT, HMAs, and intensive chemotherapy (mainly intensive anthracycline-cytarabine combinations). For patients with HR-MDS who are not a candidate for intensive chemotherapy or allo-HSCT, HMAs are the only current approved treatment option. Once patients relapse or are refractory to an HMA, there is no approved second-line therapy, and the outlook is poor with a median survival of less than 6 months ([Pratcorona 2013](#), [Prebet 2011](#), [Jabbour 2010](#)). Clinical studies are, therefore, the recommended second-line option as per NCCN and ESMO guidelines ([NCCN-MDS 2021](#), [Fenaux 2020](#)). For patients who are refractory to or have relapsed after allo-HSCT, clinical trials are also a recommended option as per the NCCN and ESMO guidelines. Therefore, patients with HR-MDS who have received at least 1 prior line of therapy are an appropriate population for this 2020-306-GLOB1 study.

4.2.2.3 Relapsed or Refractory Angio-immunoblastic T-cell Lymphoma

This study plans to enroll patients with AITL who have received at least 1 prior line of systemic anticancer therapy. For patients with relapsed/refractory (R/R) AITL, NCCN and ESMO clinical practice guidelines recommend considering a clinical study because of the poor overall survival with available salvage therapy options (NCCN-PTCL 2021, d'Amore 2015). Therefore, patients with R/R AITL who have received at least 1 prior line of therapy are an appropriate population for this 2020-306-GLOB1 study.

4.2.3 Rationale for Biomarker Testing

The mechanism of action of HMPL-306 is selective target inhibition of multiple isotypes of mIDH. Specifically, HMPL-306 is a highly selective, very potent inhibitor of mIDH. Results of local IDH mutation testing at screening will be used in further analyses.

CCI [REDACTED] and CCI [REDACTED] may be important metabolic enzymes for in vivo metabolism of HMPL-306. Therefore, mutation of CCI [REDACTED] and CCI [REDACTED] may affect PK, drug exposure, TE, and PD of the study drug. For this reason, samples collected will be tested for CCI [REDACTED] and CCI [REDACTED] as described in Section 6.1.17.

Mutant IDH isotypes (above) catalyze α -KG, and produce 2-HG – an oncogenic metabolite, accumulation of which plays a crucial role in pathogenesis of hematological malignancies in this patient population. Therefore, this study will monitor changes in levels of 2-HG in the blood. This may be useful for: i) PD and ii) correlation between PK, drug exposure, TE, and clinical response as specified in Table 1 and Section 6.1.15.

